7.1.1.2 Nocturia Impact Diary

Nocturia has wide-ranging implications for patients' quality of life, mainly through persistent, repeated sleep interruptions. Valid patient self-reported assessments of disease burden and benefit of therapy are essential to evaluate the full clinical value of treatment for the patient.

The NI Diary is a validated, nocturia-specific tool available in multiple languages and consists of a 12-item questionnaire with 11 core items (Q1-Q11) and an overall QoL impact question (Q12) (Holm-Larsen, 2014). It is used in conjunction with a voiding diary to capture patient reported consequences of nocturia and its treatment. It has a recall period of one night and day. Responses are scored from 0 to 4 (lowest to highest impact). For Question 12, response options range from 0 (not at all) to 4 (a great deal). The NI Diary total scores are calculated by summing the 11 core items. The NI Diary total and overall impact scores are standardised from 0 to 100 (lowest to highest impact).

The NI Diary will be included in the e-Diary (Section 7.1.1), which will be completed by the subjects at home, for the 3 consecutive days just prior to scheduled visits as outlined in Figure 3-2 and Figure 3-3. The NI Diary should be completed in the evening and before completing the PGI-S and PGI-I questionnaires.

One objective of this trial is to further validate the NI Diary, as well as to establish what constitutes a meaningful change in the NI Diary Total Score. Thus, the disease-specific NI Diary will be further tested and validated in connection with this trial. This will be done through psychometric validation, as described in Section 10.3.1.1, and through exit interviews, as described in Section 10.3.1.2.

7.1.1.3 Patient Reported Outcomes

The PRO instruments (questionnaires) that will be used in the trial are listed below. They should be completed in the following order:

- At home in the evening (after completion of the NI Diary):
 - Patient Global Impression of Severity (PGI-S)
 - Patient Global Impression of Improvement (PGI-I)
- At the trial site:
 - Insomnia Severity Index (ISI)
 - Bother (Hsu 5-point Likert Bother Scale)

The two PRO questionnaires that will be completed at the trial site (ISI and Hsu 5-point Likert Bother Scale) are recommended to be completed before any other assessments are performed, by the subject in a quiet place without influence from the trial personnel or accompanying family or friends. It is not permitted to help the subject choose an answer or interpret or rephrase questions which the subject does not understand. The subjects should be informed that there are no right or wrong answers and that all of the subjects' responses will remain confidential.

7.1.1.3.1 Patient Global Impression of Severity and Patient Global Impression of Disease Improvement

Patient Global Impression of Disease scales are commonly used measures of symptom severity, treatment response and the efficacy of treatments (Yalcin, 2003). The PGI-I and PGI-S will be included in the trial to indicate change or stability in global health status for anchor-based analyses to identify thresholds for clinically important changes in, e.g., NI Diary scores and number of nocturnal voids, as described in a separate Psychometric Analysis Plan (PAP). Moreover, both scales will be analysed for treatment effect, as described in Section 9.7.3. To better reflect the current condition, the revised and patient-tested versions of PGI-I and PGI-S will refer to 'night-time voiding', as compared to 'LUTS' (Viktrup, 2012).

The PGI-S is a prospective measure that measures a patient's current severity reported as "None," "Mild," "Moderate," or "Severe" (coded as 1-4). Scores on this measure will provide a patient-rated summary of the severity of the patient's nocturia symptoms.

The PGI-I is a retrospective measure. It will provide a patient-rated summary of change in nocturia since the start of trial treatment, reported as "Very much better," "Much better," "A little better," "No change," "A little worse," "Much worse," or "Very much worse," (coded as 1-7).

PGI-S followed by PGI-I will be completed by the subjects at home in the evening immediately after completing the NI Diary, as outlined in Figure 3-2 and Figure 3-3.

7.1.1.3.2 Insomnia Severity Index

Chronic disruptions of sleep will have consequences for daytime performance and well-being. Nocturia patients often report excessive daytime sleepiness, with some experiencing more severe symptoms, including increased rates of mood disorders and decrease of physical health. Fatigue is a

commonly reported symptom by individuals and causes a great amount of interferences with daily life. Sleepiness has also been linked to increased risks for accidents, such as falling asleep while driving or work-related accidents (Asplund, 2005; Ancoli-Israel, 2011).

Nocturia is characterised by shortening the FUSP. The first sleep period is of high importance due to that deepest stages of sleep (most restorative sleep) typically occur within the first few hours of the sleeping and once these stages are interrupted by waking (e.g., to void) patients are not able to make up for this during the rest of the night (Bliwise, 2015). FUSP will be a secondary endpoint in the trial.

Sleep quality will be measured through the ISI, which is an instrument to quantify the subject's perception of his/her insomnia severity. The ISI targets the subjective symptoms and consequences of insomnia as well as the degree of concern or distress caused by those difficulties (Bastien, 2001).

The ISI comprises of four 'sleep-related' items and three 'wake-related' items assessing the severity of sleep-onset and sleep maintenance difficulties (both nocturnal and early morning awakenings), satisfaction with current sleep pattern, interference with daily functioning, noticeability of impairment attributed to the sleep problem and degree of distress or concern caused by the sleep problem. Each item is rated on a 0-4 scale and the total score ranges from 0 to 28. A higher score suggests more severe insomnia.

The self-administered ISI questionnaire will be completed at the trial site by the subject before active run-in period (Visit 2), at the randomisation visit (Visit 4), after 4 weeks (Visit 6), after 8 weeks (Visit 7) and at the last trial visit after 12 weeks of treatment (Visit 8) as illustrated in Figure 3-2 and Figure 3-3. Since the ISI has a two-week recall, a reminder to think back two weeks will appear on the screen upon start of completion, in order to improve on quality of the information captured. The ISI will be completed at Visit 2 in order to compare insomnia severity to other diseases presenting with insomnia, as recorded by the ISI. The ISI completed at the remaining visits (Visits 4, 6, 7 and 8) will be used to measure treatment effect.

7.1.1.3.3 Bother

Patient bother is a broad concept covering aspects such as impact on sleep, daily life, social life, mental health, fatigue, etc. (Tikkinen, 2010). It has been shown that most nocturia patients are not very bothered by one nightly void, but that there is clearly a bother threshold at two voids or more. Moreover, comparing two adjacent voiding categories at a time, the increase was statistically significant with each increment in number of nightly voids. To further assess the change in subjective bothersomeness of nocturia, trial participants will be asked, "How much has this frequency of night-time urination bothered you?" with response options including "not at all," "slightly," "moderately," "quite a bit," and "extremely." This 5-point Likert scale has previously been used in a large epidemiological study (Hsu, 2015).

The Hsu 5-point Likert Bother Scale will be completed by the subject at the trial site at randomisation (Visit 4), after 1 week (Visit 5), after 4 weeks (Visit 6), after 8 weeks (Visit 7) and at the last trial visit after 12 weeks of treatment (Visit 8), as illustrated in Figure 3-2 and Figure 3-3.

7.1.2 Adverse Events

The procedures for collection and recording of adverse events are described in Sections 8 (Adverse Events) and 8.5 (Serious Adverse Events).

7.1.3 Clinical Laboratory Variables

Urine and blood samples for assessment of safety laboratory values (urinalysis, haematology, coagulation factors and clinical chemistry parameters including serum sodium) will be collected as presented in Table 6-1. A central laboratory will be used for the analyses (Section 7.3). Evaluation of the laboratory-based eligibility criteria will be determined by the central laboratory results. The analytical parameters are listed in Table 7-3.

Details for handling of serum sodium samples are given in Section 7.1.3.1.

Laboratory values will be reported to the investigator. Laboratory reports from the screening visit (Visit 1) must be available for evaluating the inclusion and exclusion criteria prior to the active run-in period (Visit 2) and before randomisation (Visit 4). Measurements outside normal ranges will be assessed by the investigator as ‘abnormal, not clinically significant’ or ‘abnormal, clinically significant’. Any abnormal, clinically significant changes should be reported as adverse events (Section 8.2). The laboratory reports will be signed and dated by the investigator.

Table 7-3 Safety Laboratory Variables

Clinical Chemistry	Haematology	Coagulation	Urinalysis
Alanine aminotransferase	Haemoglobin	von Willebrand Factor	Blood
Albumin	Haematocrit	Factor VIII	Glucose
Albumin/Globulin ratio	Platelet count		Ketones
Alkaline phosphatase	Red blood cell count		Urinary sediment
Aspartate aminotransferase	White blood cell count with differential count		(erythrocytes, leukocytes)
Calcium	(eosinophils, monocytes, basophils, neutrophils, lymphocytes)		pH
Chloride			Protein
Creatinine			Urobilinogen
Creatine phosphokinase			Dipstick assessment and microscopic examination will be performed. A culture will be performed in case of abnormal values.
Gamma-glutamyl transferase			
Glucose			
HbA _{1c}			
Potassium			
Sodium			
Total bilirubin			
Direct bilirubin			
Total protein			
Blood urea nitrogen			
Uric acid			
Triglycerides			

7.1.3.1 Serum Sodium

Serum sodium levels will be monitored throughout the trial as hyponatraemia is a potentially serious adverse drug reaction (ADR) associated with desmopressin treatment and may potentially be associated with FE 201836 treatment.

A central laboratory will be used. However, a local laboratory may be used in addition to the central laboratory if a quick turn-around time of the result is needed. In such case a sample must also be sent to the central laboratory. Evaluation of the laboratory-based eligibility criteria will be determined by the central laboratory results. All serum sodium values must be reviewed as soon as possible after the results are available. Any unexpected low serum sodium value must be re-tested. Any significant changes in serum sodium, judged by the investigator as clinically significant must be reported as adverse events, as described in Section 8.2.

Blood samples for analysis of serum sodium will be collected, preferably in the morning, at Visits 1, 3, 5, 6, 7 and 8, as presented in Table 6-1. The risk for subjects developing hyponatraemia during the trial period will be mitigated as follows (serum monitoring plan):

Screening (Visit 1)

All subjects must have normal serum sodium (≥ 135 mmol/L) at screening (Visit 1). If the serum sodium value is < 135 mmol/L (re-tested and confirmed, with results available within 7 days) the subject must be discontinued from the trial as a 'screening failure'.

Active Run-in Period

During the 1-week active run-in period, 4 days (± 1 day) after the planned start of IMP treatment, the subject will be telephoned to follow-up on safety.

Visit 3

At Visit 3 (after the active run-in), if the serum sodium value is < 130 mmol/L the investigator must immediately contact the subject and schedule visits for further evaluation. If the serum sodium value is < 130 mmol/L (re-tested and confirmed, with results available within 7 days) the subject will not be randomised to the trial and must be discontinued from the trial as a 'screening failure'. The subject will be followed (by the investigator) for safety until the serum sodium level is stable and not clinically significant, preferably until at least ≥ 135 mmol/L.

If the subject cannot attend Visit 3 as planned, arrangements must be made to test the serum sodium level at Day 6-8 from the IMP start date to ensure the serum sodium level is measured while the subject is taking IMP.

12-week Randomised Treatment Period

During the 12 weeks randomised treatment period, any unexpected low serum sodium value (< 135 mmol/L or a drop in serum sodium level > 10 mmol/L) must be re-tested with at least 2 additional consecutive tests to identify the nadir and duration of the hyponatraemic episode. The serum sodium level should be re-tested within 5 (± 2 days) since the previous test. The subject will be followed (by the investigator) for safety until the serum sodium level is stable and not clinically significant, preferably until at least ≥ 135 mmol/L.

Any Time Point during the Trial

If the serum sodium value is ≤ 125 mmol/L at any time point during the trial, the treatment with the IMP must be stopped immediately and the subject must be withdrawn from the trial. All cases of serum sodium values ≤ 125 mmol/L will be reported as Serious Adverse Event (SAEs) (Section 8.5). The subject will be followed (by the investigator) for safety until the serum sodium level is stable and not clinically significant, preferably until at least ≥ 135 mmol/L.

Acute Intercurrent Illness

In case of acute intercurrent illnesses characterised by fluid and/or electrolyte imbalance (such as systemic infections, fever, gastroenteritis), the treatment with IMP should be interrupted until the subject has fully recovered. The treatment can be re-started at the discretion of the investigator once the condition of the subject is stabilised.

In addition, subjects may be called in for additional unscheduled visits due to safety reason, as described in Section 6.8.

Additional Serum Sodium Testing

Events that will trigger additional serum sodium testing include, but are not limited to, the following:

- If more than 21 days elapse from the serum sodium measurement at Visit 1 and the visit date of Visit 2, the serum sodium measurement must be re-tested, with results available prior to Visit 2.
- A subject is presenting with signs or symptoms of hyponatraemia (e.g., headache, dizziness)
- A subject has gained more than 2 kilograms in body weight between visits (Section 7.2.4)
- If concomitant treatment with therapy that may induce hyponatraemia (Section 4.3.1) is initiated or dosing of an existing therapy is increased during the trial, additional serum sodium monitoring should be performed in the first week (4-8 days) after initiation and again with follow-up as judged by the investigator, at least at 4 weeks.

7.1.3.2 von Willebrand Factor and Factor VIII

Blood samples for assessment of coagulation factors will be collected at Visits 1, 4, 6 and 8.

The concentrations of the coagulation factors von Willebrand Factor (vWF) and Factor VIII (FVIII) were assessed in the phase 1 clinical trial, 000195, after both oral and intravenous administration of FE 201836. The results indicated that both vWF and FVIII were increased at high plasma concentrations of FE 201836. vWF started to increase at a plasma concentration of approximately 150 pg/mL FE 201836 and FVIII at a plasma concentration of approximately 200 pg/mL. Such high plasma concentrations are unlikely to be reached in the urological doses proposed for the present trial, however, vWF and FVIII will be measured as a safety precaution, and to ensure that these coagulation factors are not released in clinically significant amounts.

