1.3 Benefit / Risk Aspects

Benefits

Subjects enrolled in the present trial will be closely monitored and they will have the same or more frequent visits to the hospital compared to routine treatment, depending on local practice. During these visits the subjects will be given instructions regarding lifestyle changes (including limiting fluid intake). For some subjects the implementation of lifestyle changes might be enough to reduce bothersome nocturia, defined as 2 or more nocturnal voids.

Risks

Treatment of nocturia due to NP with desmopressin implies a prolonged antidiuretic effect that may be associated with an increased risk of developing hyponatraemia, especially in elderly patients. FE 201836 is designed to preserve potency at the V₂-receptor at the same level as desmopressin, with a shorter half-life, increased selectivity, faster clearance and greater extra-renal clearance compared to desmopressin. Based on the low degree of unchanged renal excretion of FE 201836, renal impairment is not expected to have any clinically relevant impact on the duration of the antidiuretic effect.

An improved safety profile is expected to result from this combination of characteristics. The short half-life of FE 201836 (approximately 2 hours) and low degree of unchanged renal excretion (approximately 5%) are designed to limit the antidiuretic effect to the night-time sleep period, when subjects do not drink or their fluid intake is limited to a minimum (to satisfy thirst only). Therefore, the risk for dilutional hyponatraemia that may occur after the subject starts drinking in the morning is expected to be low.

Subjects in the phase 1 clinical trial 000195 were dosed with up to 4800 µg (i.e., 9.6 times higher than the suggested maximum dose in the present phase 2 trial) orally without any subject being hyponatraemic. Pharmacokinetic/pharmacodynamic (PK/PD) modelling suggests that the duration of antidiuretic effect at 500 µg will be approximately 6 hours, limiting the potential for daytime antidiuresis.

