4.1.2 Exclusion Criteria

Any subject meeting one or more of the following exclusion criteria between Visit 1 (screening) through Visit 4 (randomisation) will be considered as a screening failure:

1. Current diagnosis of Obstructive Sleep Apnoea (OSA)
2. Restless Legs Syndrome (RLS)
3. Bladder Outlet Obstruction (BOO) or urine flow <5 mL/s, as confirmed by uroflowmetry upon suspicion during screening prior to Visit 2
4. Urinary incontinence defined as an average of >1 episode/day in the 3-day e-Diary prior to Visit 2 (occasional urge incontinence during daytime or at night on the way to void is not necessarily exclusionary)
5. ^c
6. Any pelvic or lower urinary tract surgery and/or radio therapy or previous pelvic irradiation within the past 6 months prior to Visit 1. Including e.g., transurethral resection for BOO or BPH, hysterectomy or female incontinence procedures
7. Genito-urinary tract pathology that can in the investigator's opinion be responsible for urgency or urinary incontinence e.g., symptomatic or recurrent urinary tract infections, interstitial cystitis, bladder-related pain, chronic pelvic pain syndrome, or stone in the bladder or urethra causing symptoms
8. A history of cancer with the last date of disease activity/presence of malignancy within the last 12 months prior to Visit 1, except for adequately treated basal cell carcinoma of the skin
9. History of any neurological disease affecting bladder function or muscle strength (e.g., Multiple Sclerosis, Parkinson's, spinal cord injury, spina bifida)
10. Habitual (fluid intake >3L per day) or psychogenic polydipsia
11. Uncontrolled hypertension, as judged by the investigator
12. ^a
13. Uncontrolled diabetes mellitus, as judged by the investigator
14. Central or nephrogenic diabetes insipidus
15. Known history of Syndrome of Inappropriate Antidiuretic Hormone (SIADH) secretion
16. History of gastric retention
17. Suspicion or evidence of congestive heart failure, (New York Heart Association [NYHA] class II, III, IV)

^c Original exclusion criterion omitted as per Clinical Trial Protocol Amendment 03 (applicable for all trial sites).

^a Original exclusion criterion omitted as per Clinical Trial Protocol Amendment 01 (applicable for all trial sites).

18. Hyponatraemia:

- Serum sodium level <135 mmol/L at Visit 1 (re-tested, with results available within 7 days)
- Serum sodium level <130 mmol/L at Visit 3 (re-tested, with results available within 7 days)

19. Hepatic and/or biliary diseases:

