- If serum sodium is <135mmol/L the test should be repeated within 7 days, if the second result is <135mmol/L the subject must be discontinued from the trial as a 'screening failure'. If more than 21 days elapse between the serum sodium measurement at Visit 1 and Visit 2, the serum sodium measurement must be re-tested, with results available prior to Visit 2.
- If serum sodium is <130mmol/L the investigator must immediately contact the subject and schedule visits for further evaluation, if the serum sodium is <130mmol/L (results confirmed within 7 days) the subject will not be randomised to the trial and must be discontinued from the trial as a 'screening failure'.
- Baseline efficacy.
- During the 1 week active run in period, 4 days (±1 day) after the planned start of IMP treatment, the subject will be telephoned to follow up on safety.
- If the subject cannot attend Visit 3 as planned, arrangements must be made to test the serum sodium level at Day 6-8 from the IMP start date.
- The end-of-trial visit (Visit 8) should be performed if the subject discontinues the trial prior to Visit 8.
- Sample to be taken preferably in the morning.

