6.4 Visit 3 Washout Period

All assessments and procedures to be performed at Visit 3 are listed below.

- Inclusion and exclusion criteria will be evaluated (specifically inclusion criterion number 9, Section 4.1.1).
- Eligible subjects will enter the 1-week Washout-period.
- The subject will be interviewed about any changes in concomitant medication and about any adverse events since the last visit.
- Body weight will be measured.
- Vital signs (blood pressure and heart rate) will be measured.
- A blood sample will be collected for analysis of serum sodium.
- Used IMP bottles, ODT blister sheets and unused IMP will be collected for drug accountability.
- The subject will be reminded about lifestyle changes (Section 4.3.3).

If the subject cannot attend Visit 3 as planned, arrangements must be made to test the serum sodium level at Day 6-8 from the IMP start date.

Prior to Visit 4 the subject will be reminded to complete the e-Diary (Section 7.1.1) for 3 consecutive days prior to the visit. The e-Diary will be reviewed for completeness (via the web-portal) by the trial site personnel.

6.5 Visit 4

All assessments/procedures to be performed at Visit 4 are listed below.

- The subject will complete the questionnaires (ISI and Bother), in the e-Diary (Section 7.1.1), at the trial site before any consultation with the trial site personnel takes place.
- Inclusion and exclusion criteria will be evaluated (specifically inclusion criterion number 10, Section 4.1.1).
- The subject will be interviewed about any changes in concomitant medication and about any adverse events since the last visit.
- A physical examination including body weight, will be performed.
- Vital signs (blood pressure and heart rate) will be measured.
- Blood samples will be drawn for analysis of haematology, clinical chemistry, coagulation factors and copeptin.
- Urine samples will be collected for urinalysis.
- Serum pregnancy test will be performed in all pre- and perimenopausal female subjects.
- Eligible subjects will be randomised to a treatment group (placebo, 500 µg FE 201836 or desmopressin up until the first interim analysis and placebo, 50-500 µg FE 201836 or desmopressin after the first interim analysis).
- The subject will be reminded about lifestyle changes (Section 4.3.3) and to wait for a minimum of 2 hours after eating their evening meal before taking the IMP.
- IMP will be dispensed (Table 5-1).

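### A Visit 3 sodium above 125 and below 130 mmol/L on the 500 µg run-in bars randomisation only if a re-test confirms it, and by inference from the schedule that re-test is drawn off drug.

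*Protocol*

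**What the plan says.** Protocol 1.3 and 9.11.1 give the one-week run-in on 500 µg the task of finding, before randomisation, subjects at raised risk of acute hyponatraemia. The sodium rule at its end is in three places:

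- **7.1.3.1, Visit 3.** If the value is below 130 mmol/L, "the investigator must immediately contact the subject and schedule visits for further evaluation". Exclusion follows only from a second result: "re-tested and confirmed, with results available within 7 days) the subject will not be randomised to the trial".
- **Table 6-1, footnote k.** The same condition: "if the serum sodium is <130mmol/L (results confirmed within 7 days) the subject will not be randomised to the trial".
- **Exclusion criterion 18 (4.1.2).** A value below 130 "mmol/L at Visit 3 (re-tested, with results available within 7 days"; here nothing is said about confirmation.

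For the first sample, 7.1.3.1 protects the on-drug state. If Visit 3 is missed, sodium must still be tested on Day 6-8 from the start of IMP, "to ensure the serum sodium level is measured while the subject is taking IMP". No such condition is set for the re-test.

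At Visit 3 the run-in ends: "Used IMP bottles, ODT blister sheets and unused IMP will be collected for drug accountability" (6.4). Table 5-1 shows no treatment in the washout, and IMP is next dispensed at Visit 4. A single value of 125 mmol/L or less forces withdrawal with no confirmation (4.4 and 7.1.3.1).

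**The concern.** A fall in sodium that appears on 500 µg and reverses when the drug stops is the signal the run-in exists to detect. If the confirming sample is drawn in washout, the rule clears that subject. It excludes only those whose sodium stays low without drug, together with those at 125 or less.

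Elsewhere the plan takes the same single value seriously. The Definition of Terms treats a sodium below 130 as clinically significant. Protocol 9.10.3 and SAP Table 7 count one such run-in observation as a hyponatraemia episode. The run-in trigger for the DMC (9.11.1) counts values below 130 and mentions no confirmation. One subject can therefore be a counted run-in case and still be randomised, possibly to 500 µg.

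After randomisation the position differs. IMP must be stopped only at 125 or less, so re-tests of a value of 126-129 are by default done on drug. It is the pre-randomisation check that is settled off drug. What is at stake is patient safety, not the efficacy result.

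**Working it through.** **The plan's own figure.** The only numerical rule tied to run-in sodium below 130 is Table 9-7. Exact (Clopper-Pearson) two-sided 95% lower limits for 4/10, 6/20, 10/50, 17/100 and 30/200 are 12.16%, 11.89%, 10.03%, 10.23% and 10.35%. These agree with the table's 12.2, 11.9, 10.0, 10.2 and 10.4. That rule acts at trial level; the point here does not depend on it.

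**Is the re-test off drug?** This is an inference.
1. Eligibility rests on the central laboratory, and a low result leads to contacting the subject and arranging further visits. The subject has normally left by then.
2. IMP has been handed back, and none is scheduled between Visit 3 (Day -7) and Visit 4 (Day 1). With no Day 0 that is 7 nights, so a re-test *d* days after Visit 3 follows *d* drug-free nights, *d* = 1 to 7.
3. On elimination, 1.3 says: "The short half-life of FE 201836 (approximately 2 hours". Half-lives elapsed = hours since last dose / 2. The documents give no clock times, so these are assumed for a next-day re-test:

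| Last dose | Sample | Hours | Half-lives |
|---|---|---|---|
| 22:00 | 09:00 | 11 + 24 = 35 | 17.5 |
| 24:00 | 08:00 | 8 + 24 = 32 | 16 |
| 21:00 | 12:00 | 15 + 24 = 39 | 19.5 |

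At 16 half-lives, 2^-16 = 0.0015% of the drug remains.

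**What the rule does with recovery (illustration).** Let *m* be the true sodium at re-test and *s* the total SD, assumed to be 1.5 to 2.5 mmol/L because the documents give none. P(re-test < 130) = Φ((130 − *m*)/*s*).
- *m* = 128, no recovery: 0.79 to 0.91.
- *m* = 132: 0.09 to 0.21.
- *m* = 135: at most 0.023.

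Under these assumptions, a subject who recovers even to 132 is excluded at most about one time in five.

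**Where a cleared subject goes (3.3 ratios).**
- First 125 at 2:2:1: 50 placebo, 50 on 500 µg, 25 desmopressin. Active 75/125 = 60%, of which 40 points are 500 µg.
- Next 175 at 2:7:1: 35 placebo, 122.5 FE 201836 (50-500 µg), 17.5 desmopressin. Active 140/175 = 80%.
- If all 300 are randomised: (75 + 140)/300 = 71.7%.

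**Doses before the next scheduled on-drug sodium.** The first dose is on the night of Day 1, and Visit 5 is on Day 8±2. Day 6, 8 or 10 gives 5, 7 or 9 doses.

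**Other safeguards.** None sets a fixed limit before randomisation for values above 125 and below 130. Criterion 24 and the safety withdrawal in 4.4 are discretionary. SRC review, central monitoring and the DMC trigger act on the trial. Follow-up until stable, and tests prompted by symptoms or weight gain, carry no eligibility limit. The Visit 4 sodium (SAP Table 3, footnote b) is off drug and has no threshold attached.

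**The case against.** The strongest points on the other side are these.

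- **The timing is not in the text.** True. A same-day redraw after a local-laboratory result, or a quick re-test when Visit 3 was missed, could share the on-drug state. Criterion 18 omits confirmation, so a strict reader might exclude on the first value. But 7.1.3.1 and footnote k both require confirmation, and the ordinary schedule puts the re-test in washout. The disagreement in wording is itself worth repairing.
- **Half-lives describe drug, not sodium.** Also true. No recovery time is given, so a next-day sodium may still be low. The modelled antidiuretic effect at 500 µg lasts about 6 hours (1.3), so a morning Visit 3 sample may itself fall after it. The relevant contrast is a morning after a dosed night against one after an undosed night, and the point is limited to falls that do recover.
- **The trial tolerates 126-129 after randomisation.** It does, under monitoring. That does not explain why a pre-randomisation screen of drug response should be decided by a drug-free sample.
- **Confirmation guards against error.** It does, but an off-drug sample cannot tell laboratory error from recovery. A repeat assay on the same sample checks analytical error without changing the drug state.
- **The episode counts are for reporting.** SAP Table 7 starts an episode at the first observation in both periods; only the confirmed category needs more. The counting contrast is therefore supporting evidence and not the core of the point.
- **The number affected may be very small.** This stands. In phase 1, doses up to 4800 µg were given "orally without any subject being hyponatraemic" (1.3), though to young healthy subjects.

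**Conclusion.** The concern holds and should be fixed. For values above 125 and below 130 mmol/L, the fixed rule lets through a subject whose sodium falls on 500 µg and recovers off drug, contrary to the run-in's stated purpose. This rests on the inference that the re-test is normally drawn in washout, and it applies only to subjects who recover before that draw.

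The number of subjects cannot be estimated. The documents give neither the on-drug rate of such values nor the share that recovers. What is known is the exposure of a subject who passes: 60% active before the first interim, 80% after, and 5 to 9 doses before the next scheduled on-drug sodium if on an active arm. The allocation figures are not a measure of risk, since they pool 50 µg with 500 µg and desmopressin. Power, error rates and the efficacy analysis are unaffected.

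**What to change.** In the second bullet of exclusion 18 (and its copy in the synopsis), in Table 6-1 footnote k, and under Visit 3 in 7.1.3.1, make the on-drug value decisive. For example: a central-laboratory serum sodium under 130 mmol/L in the Visit 3 sample, drawn on IMP, means the subject is not randomised.

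To guard against analytical error, have the central laboratory repeat the assay on that same sample before the result counts. Section 7.3 has samples destroyed once results are available. Add there, or in the laboratory manual, that a Visit 3 sample reading below 130 is kept until the repeat is reported. Keep washout re-tests for safety follow-up only.

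The cost is a few lines of wording, with no extra visit, tube or dose. There would be a few more screening failures, including an occasional false one from a collection or labelling error that a same-sample repeat cannot detect. Removing a few more sodium-sensitive subjects may also slightly lower the incidence shown in the therapeutic-window plots. That effect should be small, because the plan already intends to exclude such subjects.
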